5.8. Interim Analyses

An internal independent interim analysis committee (IAC) will be established to review the interim data including data from the LTE available at the time of the IA to formulate recommended decisions and/or actions in accordance with the objectives of the interim analyses. The IAC will consist of at least a clinician and a statistician (neither of whom are involved in study conduct), one of whom will chair the committee, and other members as required. The details will be provided in a separate IAC charter.

The IAC will review the unblinded efficacy data and provide recommendations about the next step of study conduct and the future development of the compound based upon the results of the first (when approximately 50% (n=120) of the participants reach Week 4) and/or second (when approximately 2/3 (n=160) of the participants reach Week 16) interim efficacy analyses. The first IA will be for nonbinding futility and to inform the planning for the clinical development for JNJ-77242113 for other indications based on the proportion of participants achieving PASI 50 response at Week 4. The second IA will be used for planning of future psoriasis studies and will be based on the primary endpoint which is the proportion of participants achieving PASI 75 response at Week 16. Other selected supportive efficacy endpoints could also be reviewed. The unblinded results will be limited to specific sponsor personnel not involved in the study conduct. Interim analysis results will not be disseminated to investigators or individuals associated with the conduct of the study.

Details of the plan for the interim analyses will be specified in the Interim Analysis SAP.

5.8.1. Data Monitoring Committee (DMC) or Other Review Board

An external independent data monitoring committee (iDMC) whose members are not directly involved in the conduct of the 77242113PSO2001 and 77242113PSO2002 studies, will review unblinded safety data to ensure the safety of the participants enrolled in this study. The committee will meet regularly to review unblinded safety data. After the review, the iDMC will make recommendations to the sponsor regarding the conduct of the study. The iDMC will consist of at least one clinical physician and one statistician, not involved in the conduct of the study. The iDMC responsibilities, authorities, and procedures will be documented in the iDMC charter.

An independent, external DMC has been established to monitor data on an ongoing basis to ensure the continuing safety of the participants enrolled in this study. The DMC consists of 3 members (including 1 dermatologist, one cardiologist and one statistician) who are independent of the sponsor. None of the members is participating as an investigator in the current study.

The major function of the DMC is to monitor the safety of the study agent by reviewing the serious adverse events (SAEs) each month and by reviewing the study safety data approximately every 4 months. The content of the safety summaries for this study are defined and documented in the DMC SAP developed by the sponsor. No hypothesis testing will be conducted. An independent statistical supporting group, provided by SGS, supports the DMC and is the liaison between sponsor and the DMC.

In addition, the DMC roles and responsibilities, and the general procedures (including communications) are defined and documented in the Data Monitoring Plan developed by the sponsor detailing the safety data monitoring to be conducted by the DMC.

6. SUPPORTING DOCUMENTATION

6.1. Appendix 1 List of Abbreviations

ADA	anti-drug antibody
AE	adverse event
ALT/SGPT	alanine aminotransferase
AST/SGOT	aspartate aminotransferase
ATC	anatomic and therapeutic class
AUC	area under the curve
BID	twice daily
BMI	body mass index
BSA	body surface area
CI	confidence interval
Cmax	maximum concentration
CRF	case report form
CSR	Clinical Study Report
CTCAE	Common Terminology Criteria for Adverse Events
CV	coefficient of variation
DLQI	Dermatology Life Quality Index
DMC	Data Monitoring Committee
DPS	Data Presentation Specifications
eCRF	electronic case report form
F (%)	absolute SC bioavailability
FAS	full analysis set
FDA	Food and Drug Administration
f-PGA	Fingernail Physician's Global Assessment
GenPs-SFQ	Genital Psoriasis Sexual Frequency Questionnaire
GMS	Global Medical Safety
hf-PGA	Physician's Global Assessment of Hands and/or Feet
IA	Interim analysis
IAC	Interim analysis Committee
IAS	Interim analysis set
ICH	International Conference on Harmonisation
IGA	Investigator Global Assessment
IQ	interquartile
IWRS	interactive web response system
LLOQ	lower limit of quantification
LTE	long-term extension
PK	pharmacokinetic(s)
QD	once daily
MedDRA	Medical Dictionary for Regulatory Activities
MMRM	Mixed-Effect Model Repeated Measure
MRD	minimum required dilution
NAb	neutralizing antibodies
NAPSI	Nail Psoriasis Area and Severity Index
PASI	Psoriasis Area and Severity Index
PD	pharmacodynamic(s)
PI	principal investigator
PK	pharmacokinetic(s)
PP	per protocol
PRO	patient-reported outcome(s) (paper or electronic as appropriate for this study)
PROMIS-29	Patient-Reported Outcomes Measurement Information System-29
PSSD	Psoriasis Symptom and Sign Diary
QD	once daily
SAE	serious adverse event
SAP	Statistical Analysis Plan
SD	standard deviation

SMQs	standardised MedDRA queries
TEAE	treatment-emergent adverse event
T _{max}	time to maximum concentration
US NCI	United States National Cancer Institute
V	volume distribution
V _z	volume of distribution based on terminal phase
V _{z/F}	apparent volume of distribution based on terminal phase after extravascular administration
WHO	World Health Organization
WHO-DD	World Health Organization Drug Dictionary
PGI-C	Patient Global Impression-Change
PGI-S	Patient Global Impression-Severity
s-PGA	Static Physician's Global Assessment
ss-IGA	Scalp Specific Investigator Global Assessment
TSQM-9	Treatment Satisfaction Questionnaire for Medications-9 items
TYK	tyrosine kinase
ULN	upper limit of normal
US	United States
WBC	white blood cell

6.2. Appendix 2 Changes to Protocol-Planned Analyses

N/A

6.3. Appendix 3 Demographics and Baseline Characteristics

For study 77242113PSO2001, the number of participants in each analysis set will be summarized and listed by intervention group, combined active intervention group, and overall. In addition, the distribution of participants by region, country, and site ID will be presented unless otherwise noted.

Table 7 presents a list of the demographic variables that will be summarized by intervention group, combined active intervention group, and overall for the FAS analysis set.

Table 7: Demographic Variables

Continuous Variables:	Summary Type
Age (years)	Descriptive statistics (N, mean, standard deviation [SD], median and range [minimum and maximum], and IQ range).
Weight (kg)	
Height (cm)	
Body Mass Index (BMI) (kg/m ²)	
Categorical Variables	
Age (<45 years, 45-64 years, and >=65 years)	
Sex (male, female)	
Weight (<90 kg, >=90 kg)	
Race (American Indian or Alaska Native, Asian, Black or African American, Native Hawaiian or other Pacific Islander, White, Unknown, Not Reported)	Frequency distribution with the number and percentage of participants in each category.
Ethnicity (Hispanic or Latino, not Hispanic or Latino)	
BMI ([normal <25 kg/m ² , overweight 25-<30 kg/m ² , obese >=30 kg/m ²])	

^a If multiple race categories are indicated, the Race is recorded as 'Multiple'

Baseline disease characteristics (e.g., duration of psoriasis disease, , baseline PASI score, baseline IGA score, baseline BSA, baseline PRO related measurements, and baseline regional psoriasis related measurements) will be summarized by treatment group. In addition, summaries of participants' medical history and current diagnoses, alcohol intake, and smoking status will be provided by treatment group will also be provided.

Since study 77242113PSO2002 is the LTE of study 77242113PSO2002, the summaries specified above will only be done for study 77242113PSO2001.

6.4. Appendix 4 Protocol Deviations

In general, the following list of major protocol deviations may have the potential to impact participants' rights, safety or well-being, or the integrity and/or result of the clinical study. Participants with major protocol deviations will be identified prior to database lock and the participants with major protocol deviations will be summarized by category through Week 16 and through the end of study.

- Developed withdrawal criteria but not withdrawn
- Entered but did not satisfy criteria
- Received a disallowed concomitant treatment
- Received wrong treatment or incorrect dose
- Other

A listing of participants with major protocol deviations will also be provided by randomized treatment group. In addition, analyses of COVID-19 related protocol deviations will be provided.

6.5. Appendix 5 Prior and Concomitant Medications

Prior medications are defined as any therapy used before the day of first dose (partial or complete) of study intervention. Previous psoriasis medications/therapy will be summarized by intervention group.

Concomitant medications will be coded using the World Health Organization Drug Dictionary (WHO-DD). Concomitant medications are defined as any therapy used on or after the same day as the first dose of study intervention, including those that started before and continue on after the first dose of study intervention.

Summaries of concomitant medications will be presented by anatomic and therapeutic class (ATC) term, and intervention group. The proportion of participants who receive each concomitant medication will be summarized as well as the proportion of participants who receive at least 1 concomitant medication.

Participants' psoriasis medication history with topical agents, phototherapy, non-biologic systemic therapies, and biologic medications will be summarized by treatment group for all randomized participants. If data are available, total cumulative duration of treatment with these medications will be summarized. In addition, reasons for which participants discontinued previous systemic therapies (contraindication, inadequate response, intolerance [ie, AEs], or other) will be summarized by randomized treatment group.

The number of participants who received concomitant treatment of moisturizer for psoriasis will be summarized by randomized treatment group.

Participants who received concomitant corticosteroids for indications other than psoriasis and/or psoriatic arthritis will be listed. Participants with concomitant prophylactic treatments for latent TB infection will also be listed.

6.6. Appendix 6 Medical History

Summaries of participants' medical history, general medical history, alcohol intake, and smoking status will be provided by treatment group. In addition, the distribution of participants by prior biologic use (yes/no) and type of biologic therapy will also be provided.

6.7. Appendix 7 Intervention Compliance

Treatment compliance will be assessed based through Week 16 on the full analysis set (FAS) for study 77242113PSO2001 and through Week 52 (Week 36 of the 77242113PSO2002 study) on full analysis set for study 77242113PSO2002. Descriptive summaries (sample size, mean, standard deviation, median, and range) will be presented for the percent of compliance defined as the number of tablets taken divided by the number of tablets that should have been taken. Overall compliance will be categorized as $> 120\%$, 80 to $\leq 120\%$, and $< 80\%$. In addition, treatment compliance will be assessed by summarizing the protocol deviation of the study agent administration related to incorrect study agent or dose received and missed administrations.

6.8. Appendix 8 Extent of Exposure

The extent of exposure will be summarized for randomized participants that received at least one study agent administration. Descriptive statistics (N, mean, SD, median, IQ range, and range) for treatment duration (weeks), cumulative dose (mg), and average daily dose (mg/day) will be presented by treatment groups. The average daily dose (mg/day) for each dose regimen (25 mg QD, 50 mg QD, 25 mg BID, 100 mg QD, 100 mg BID) is calculated as:

Number of the total active tablets taken x tablet's strength (25 mg or 100 mg) / (the last dose date – the first dose date +1)

In addition, distribution of participants through Week 16 and through Week 52 (Week 36 of the 77242113PSO2002) by study agent lot will be analyzed for 77242113PSO2001 and 77242113PSO2002 respectively.

6.9. Appendix 9 Adverse Events of Special Interest

Not Applicable.

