 - A participant undergoing evaluation has chest imaging with evidence of current active TB and/or a positive IGRA test result, unless active TB can be ruled out and appropriate treatment for latent TB can be initiated prior to the next administration of study intervention and continued to completion. Indeterminate/borderline results should be handled as outlined in Section [8.2.8](#).
 - A participant receiving treatment for latent TB discontinues this treatment prematurely or is noncompliant with the therapy
- The participant is unable to adhere to the study visit schedule or comply with protocol requirements.
- The participant has a possible Hy's Law case, as defined by the occurrence of alanine aminotransferase (ALT) or aspartate aminotransferase (AST) $\geq 3 \times \text{ULN}$, together with total bilirubin $\geq 2 \times \text{ULN}$ or International Normalized Ratio (INR) > 1.5 (if measured) without an identifiable cause (Section [10.9](#)).
- The participant has his/her treatment assignment unblinded by the investigator.
- Sponsor decision.

Discontinuation of a participant's study intervention should be considered for participants with any type of suicidal ideation or behavior, or any self-injurious behavior, who are deemed to be at risk by the investigator. Discussion of such participants with the medical monitor or designee is required.

For participants who report Suicidal Ideation with Intention to Act ("Ideation level 4"), suicidal ideation with specific plan and intent ("Ideation level 5"), suicidal behavior (actual suicide attempt, interrupted suicide attempt, aborted suicide attempt, or preparatory behaviors for making a suicide attempt) or any self-injurious behavior on a post-baseline C-SSRS assessment, the investigator risk assessment must be based upon evaluation by a mental health professional (Section 10.7).

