8.3.7. Adverse Events of Special Interest

An adverse event of special interest (AESI; serious or non-serious) is one of scientific and medical concern specific to the sponsor's product or program, for which ongoing monitoring and expedited communication (within 24 hours) by the investigator to the sponsor is warranted. The AESIs for JNJ-77242113 are, active TB, malignancy, and potential Hy's Law cases.

Any newly identified malignancy, case of active TB, or potential Hy's law case occurring after the first study intervention administration(s) must be reported by the investigator according to the procedures in Section 10.6). Investigators are also advised that active TB is considered a reportable disease in most countries. These events are to be considered serious only if they meet the definition of an SAE.

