9.4.5. Safety Analyses

Safety data, including but not limited to, AEs, SAEs, AESIs (active TB, malignancy, potential Hy's Law cases), discontinuation of study intervention due to AEs, changes in laboratory assessments, changes in vital signs, and changes in weight will be summarized. Intervention-emergent AEs will be summarized by treatment group and Medical Dictionary for Regulatory Activities (MedDRA) system organ class and preferred terms. Details will be specified in the SAP.

Adverse Events

The verbatim terms used in the eCRF by investigators to identify AEs will be coded using the MedDRA. Intervention-emergent AEs are AEs with onset during the intervention period or that are a consequence of a preexisting condition that has worsened since baseline. All intervention-emergent AEs will be included in the analysis. For each AE, the percentage of participants who experience at least 1 occurrence of the given event will be summarized by intervention group. In addition, comparisons between intervention groups will be provided if appropriate.

The following analyses will also be used to assess the safety of participants in the study:

- The incidence and type of AEs.
- The incidence and type of SAEs.
- The incidence and type of severe AEs.
- The incidence and type of related AEs as assessed by the investigator.
- The incidence and type of AEs leading to discontinuation of study.

Listings of participants with SAEs, severe AEs, AEs for psoriasis, AEs leading to discontinuation of study and anaphylactic reaction/serum sickness reactions will also be provided. All safety analyses will be based on the population of participants who received at least 1 administration of study intervention; participants will be summarized by the intervention they received.

Clinical Laboratory Tests

Laboratory data will be summarized by type of laboratory test (eg, hematology, clinical chemistry). Selected laboratory parameters will be summarized by treatment groups. Common Terminology Criteria for Adverse Events (CTCAE) and ULN will be used to identify abnormal laboratory test results, and the incidence and severity of abnormal laboratory parameters (hematology and chemistry) will be summarized by treatment group.

In addition, a listing of participants with Grade 2 or higher laboratory test results (based on the CTCAE criteria) will also be provided.

C-SSRS

Suicide-related thoughts and behaviors based on the C-SSRS will be summarized descriptively by treatment group.

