5.6.3. Additional Safety Assessments (if applicable)

5.6.3.1. Clinical Laboratory Tests

Clinical laboratory tests will be displayed for the participants included in the safety analysis set.

Descriptive statistics and graphical displays will be presented for selected chemistry and hematology laboratory tests at scheduled time points.

Change from baseline through different study periods in both studies as specified in Section 5.6 will be summarized for chemistry, and hematology tests and displayed by intervention group. Box plots of laboratory measurements and change from baseline will be provided for the selected laboratory measurement.

- **Hematology** will include but are not limited to the following: Basophils, Eosinophils, Hemoglobin, Lymphocytes, Monocytes, Neutrophils, Platelets, WBC, CRP and ESR.
- **Chemistry** will include but are not limited to the following: ALT, AST, Albumin, Alkaline Phosphatase, Bicarbonate (CO₂), Corrected Calcium, Chloride, Creatinine, GGT, Glucose, Potassium, SGOT, SGPT, Sodium, Total Bilirubin, Total Protein, Urea Nitrogen.

Applicable laboratory results will be graded according to National Cancer Institute's Common Terminology Criteria for Adverse Events (NCI-CTCAE). The proportion of participants with post-baseline values by maximum toxicity grade for clinical laboratory tests will be summarized by study intervention group. Participants with toxicity grades ≥ 2 will be listed.

In addition, for selected laboratory parameters, ULN will also be used to identify abnormal laboratory test results, and the incidence and severity of abnormal laboratory parameters (hematology and chemistry) will be summarized by treatment group. Participants with maximum post-baseline elevated liver function tests through Week 16 (77242113PSO2001) and through Week 56 relative to ULN will be summarized in categories as shown below will be provided.:

- $> 1 \times$ ULN
- $\geq 3 \times$ ULN
- $\geq 5 \times$ ULN
- $\geq 10 \times$ ULN

- $\geq 20 \times \text{ULN}$

In addition, Summary of potential Hy's Law case (ALT or AST $\geq 3 \times \text{ULN}$ and total bilirubin $\geq 2 \times \text{ULN}$) through Week 16 and Week 56 respectively will also be provided.

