Alkaline phosphatase increased	>ULN - 2.5 x ULN if baseline was normal; 2.0 - 2.5 x baseline if baseline was abnormal	>2.5 - 5.0 x ULN if baseline was normal; >2.5 - 5.0 x baseline if baseline was abnormal	>5.0 - 20.0 x ULN if baseline was normal; >5.0 - 20.0 x baseline if baseline was abnormal	>20.0 x ULN if baseline was normal; >20.0 x baseline if baseline was abnormal	Ranges defined for “abnormal baseline” are applied only if baseline > ULN. If baseline < LLN, then ranges for “normal baseline” are applied.
Aspartate aminotransferase increased	>ULN - 3.0 x ULN if baseline was normal; 1.5 - 3.0 x baseline if baseline was abnormal	>3.0 - 5.0 x ULN if baseline was normal; >3.0 - 5.0 x baseline if baseline was abnormal	>5.0 - 20.0 x ULN if baseline was normal; >5.0 - 20.0 x baseline if baseline was abnormal	>20.0 x ULN if baseline was normal; >20.0 x baseline if baseline was abnormal	Ranges defined for “abnormal baseline” are applied only if baseline > ULN. If baseline < LLN, then ranges for “normal baseline” are applied.
Blood bilirubin increased	>ULN - 1.5 x ULN if baseline was normal;	>1.5 - 3.0 x ULN if baseline was normal;	>3.0 - 10.0 x ULN if baseline was normal;	>10.0 x ULN if baseline was normal;	Ranges defined for “abnormal baseline” are

CTCAE Term	Grade 1	Grade 2	Grade 3	Grade 4	Janssen implementation notes
	> 1.0 - 1.5 x baseline if baseline was abnormal	>1.5 - 3.0 x baseline if baseline was abnormal	>3.0 - 10.0 x baseline if baseline was abnormal	>10.0 x baseline if baseline was abnormal	applied only if baseline > ULN. If baseline < LLN, then ranges for “normal baseline” are applied.
CD4 lymphocytes decreased	<LLN - 500/mm ³ ; <LLN - 0.5 x 10 ⁹ /L	<500 - 200/mm ³ ; <0.5 - 0.2 x 10 ⁹ /L	<200 - 50/mm ³ ; <0.2 x 0.05 - 10 ⁹ /L	<50/mm ³ ; <0.05 x 10 ⁹ /L	
Cholesterol high	>ULN - 300 mg/dL; >ULN - 7.75 mmol/L	>300 - 400 mg/dL; >7.75 - 10.34 mmol/L	>400 - 500 mg/dL; >10.34 - 12.92 mmol/L	>500 mg/dL; >12.92 mmol/L	
CPK increased	>ULN - 2.5 x ULN	>2.5 x ULN - 5 x ULN	>5 x ULN - 10 x ULN	>10 x ULN	
Creatinine increased	Creatine Kinase >ULN - 1.5 x ULN	Creatine Kinase >1.5 - 3.0 x baseline; >1.5 - 3.0 x ULN	Creatine Kinase >3.0 x baseline; >3.0 - 6.0 x ULN	Creatine Kinase >6.0 x ULN	

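### The SAP plans no AESI output for active TB or malignancy, writes its creatinine grading row on creatine kinase, and the documents carry conflicting Hy's Law definitions

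*SAP*

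**What the plan says.** **AESIs.** Protocol 8.3.7 states: "The AESIs for JNJ-77242113 are, active TB, malignancy, and potential Hy's Law cases". Protocol 9.4.5 puts them among the data to be summarized ("Safety data, including but not limited to, AEs, SAEs, AESIs (active TB, malignancy, potential Hy's Law cases), discontinuation of study intervention due to AEs") and leaves details to the SAP. SAP Appendix 9 (6.9), on AESIs, says "Not Applicable". SAP 5.6.2 lists five summary tables: all, serious, leading to discontinuation of study intervention, severe, and related. Its listings cover serious, severe, discontinuation, psoriasis, suicidality, anaphylactic or serum sickness events, and deaths. None is for AESIs, TB or malignancy. SAP Appendix 2 (6.2), on changes from the protocol's analyses, is marked N/A.

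**Creatinine grading.** In SAP Appendix 11 (6.11) the row for increased creatinine begins "Creatine Kinase >ULN - 1.5 x ULN" and names creatine kinase in its other three grades too. The row above it already grades CPK, the same enzyme.

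**Hy's Law.** SAP 5.6.3.1 summarizes potential cases, defined as ALT or AST at least 3 x ULN with total bilirubin at least 2 x ULN, "through Week 16 and Week 56 respectively will also be provided". Protocol Appendix 2 (10.2) uses the same rule. Protocol 7.1 and Protocol Appendix 9 (10.9.2.1) also accept INR above 1.5, if measured, in place of the bilirubin criterion. Footnote 2 of 10.9.2.1 adds ALP below 2 x ULN.

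**The concern.** The protocol delegates the AESI details to the SAP, and the SAP says there is nothing to specify. A programmer following the SAP would build no display that collects malignancies or active TB cases by treatment group. A reader of the study report would have to assemble them from preferred terms. Malignancy has no single preferred term, and Protocol 8.3.7 treats an AESI as serious only if it separately meets the SAE definition, so the SAE table and listing are not a complete substitute.

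The creatinine row matters because the Appendix 11 grades feed the table of maximum toxicity grade and the listing of Grade 2 or higher in SAP 5.6.3.1. Applied as written, it gives CK two grades and creatinine none.

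The Hy's Law passages matter because this is one of the three AESIs, and a given participant can be a case in one section and not in another.

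Protocol 2.3 says this is the first study of the compound in psoriasis and that benefit-risk is not yet established, so the safety displays should match what the protocol promised.

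**Working it through.** The plan gives no figure to reproduce here. The check sets the passages side by side and applies the written rules to illustrative values.

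**1. AESIs**

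| AESI in Protocol 8.3.7 | Own output in the SAP | Where it otherwise appears |
|---|---|---|
| Active TB | None | General adverse event tables; serious or severe outputs if it qualifies |
| Malignancy | None | Same |
| Potential Hy's Law case | Summary in 5.6.3.1 | – |

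So two of the three lack a dedicated output, and SAP Appendix 2 does not declare this as a change.

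**2. The two rows worded on CK**

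Upper limits of Grades 1, 2 and 3 in multiples of ULN: CPK row 2.5, 5, 10; creatinine row read literally 1.5, 3.0, 6.0. Only the ULN limits are used; the creatinine row also has baseline multiples in Grades 2 and 3.

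| CK (x ULN) | CPK row | Creatinine row, literal |
|---|---|---|
| 1.5 | 1 | 1 |
| 2 | 1 | 2 |
| 3 | 2 | 2 |
| 4 | 2 | 3 |
| 6 | 3 | 3 |
| 7 | 3 | 4 |
| 12 | 4 | 4 |

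The rows disagree by one grade when CK is above 1.5 and up to 2.5, above 3.0 and up to 5, and above 6.0 and up to 10 x ULN. In the lowest of these bands the literal reading brings a participant into the Grade 2 or higher listing who is Grade 1 on the CPK row. No row then grades serum creatinine, which Protocol Appendix 2 includes in the chemistry panel.

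**3. Hy's Law rules**

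Rule A (SAP 5.6.3.1, Protocol Appendix 2): ALT or AST ≥3 x ULN and bilirubin ≥2 x ULN.
Rule B (Protocol 7.1): ALT or AST ≥3 x ULN and (bilirubin ≥2 x ULN or INR >1.5 if measured), with no identifiable cause, assumed met below.
Rule C (Protocol 10.9.2.1, footnote 2): ALT or AST ≥3 x ULN and (bilirubin ≥2 x ULN or INR >1.5 if measured), with ALP <2 x ULN.

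| ALT, bilirubin, ALP (x ULN); INR | A | B | C |
|---|---|---|---|
| 4, 2.5, 1; not measured | Yes | Yes | Yes |
| 4, 1.2, 1; 1.8 | No | Yes | Yes |
| 4, 2.5, 2.5; 1.8 | Yes | Yes | No |
| 4, 1.2, 2.5; 1.8 | No | Yes | No |

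The SAP rule is narrower than B and C on INR and wider than C on ALP. Protocol Appendix 2 also refers to Section 8.3.1 for reporting of such cases, but that section has no Hy's Law text.

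**The case against.** **AESIs.** Potential Hy's Law cases are summarized, and SAP 5.6.2 includes every treatment-emergent event, so TB and malignancy cannot vanish from the report. Protocol 9.4.5 promises that AESIs will be summarized, not that there will be a dedicated table. All of this stands. It limits the fault to the missing grouping of two AESIs, an appendix that contradicts the protocol, and an undeclared departure.

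**Creatinine.** The row's own term is creatinine, CPK has a separate row, and Appendix 11 is stated to follow CTCAE v5.0, so this is very probably a label slip. Creatinine change from baseline is summarized regardless. That stands, but the slip is in the specification from which grades are programmed. The protocol defines no creatinine event, so this is an error internal to the SAP.

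**Hy's Law.** The SAP matches Protocol Appendix 2 exactly. INR is not in the routine panel and is obtained in liver-event follow-up, where ALT or AST is already at least 3 x ULN, a category the SAP displays. INR above 1.5 is at least Grade 2 in SAP Appendix 11, so a value in the graded data is listed. The fault is therefore inconsistency between passages, and it cannot be put down to the SAP alone.

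**Stronger readings the documents do not support.** A reader might infer that bilirubin between 2 and 3 x ULN shows only as above 1 x ULN, because the SAP's liver categories step from >1 to ≥3. With a normal baseline, Appendix 11 makes that Grade 2, so it enters the grade table and the listing. The Hy's Law summary also applies the 2 x ULN bilirubin threshold directly. A reader might also infer that dose selection depends on these outputs. Protocol 9.4.1 links dose selection to MCP-Mod on PASI 75, and SAP 5.8.1 places the monitoring committee's summaries in a separate plan.

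**Conclusion.** The point holds at moderate weight. Two of the three protocol AESIs have no output of their own in the SAP, against an explicit protocol commitment and with no declared change. The creatinine row is wrong as written. Followed literally, it gives CK a second, conflicting grade over three ranges (above 1.5 to 2.5, above 3.0 to 5, and above 6.0 to 10 x ULN) and leaves creatinine ungraded. The Hy's Law item is a reconciliation matter: three rules are in use, and the SAP's agrees with one part of the protocol and not with others.

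This does not show that events would be lost from the report. TB and malignancy stay in the general tables, and creatinine stays in the change-from-baseline summaries. The size of the creatinine effect assumes the cell text is programmed as it stands; a programmer who recognised the slip would avoid it. The Hy's Law examples are illustrative values, and the documents give no basis for estimating how many participants would be affected.

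**What to change.** 1. Replace the entry in SAP Appendix 9 with the three AESIs of Protocol 8.3.7. In SAP 5.6.2 add a by-group summary and a listing for active TB and malignancy, stating how the terms are identified, and refer to 5.6.3.1 for Hy's Law.
2. In SAP Appendix 11, make the row for increased creatinine refer to creatinine in all four grades, and leave the CPK row as the only one for creatine kinase.
3. Reconcile the Hy's Law wording across Protocol 7.1, Protocol Appendix 2, Protocol Appendix 9 (10.9.2.1 with footnote 2) and SAP 5.6.3.1, and correct the reference in Protocol Appendix 2 to Section 8.3.1. Which definition applies is for the sponsor to settle. As a descriptive display only, show participants who meet the INR criterion (if measured) on a separate line, with ALP status.

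Cost: SAP wording, protocol wording where the reconciliation requires it, and a few table rows and one listing. No new data are needed.
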